The primary efficacy endpoint will also be evaluated in the ITT, Implanted analysis set, Responder analysis set, and the Per Protocol analysis set (without imputation for missing data) to assess the robustness of results. If there are no differences between analyses sets (e.g., Implanted and Responder analysis sets include all the same subjects), separate analyses will not be presented. Analyses of the primary efficacy endpoint for all analysis populations will be conducted after 6-month post-implant follow-up is completed for all subjects.

The primary efficacy endpoint will be presented by study visit with descriptive statistics and nominal 95% confidence intervals.

5.6.2.2 Additional Analyses

Subgroup analysis of the primary efficacy endpoint will be performed for the following subgroups: sex, age (Age<65, Age≥65), race (white vs. non-white), baseline UUI episodes, site, and region (US vs. OUS). These analyses are intended to demonstrate consistency of results across subgroups. At each level of the subgroup of interest, the within group estimates will be summarized with frequency counts and percentages. The subgroup analysis of the primary efficacy endpoint are regarded as exploratory and will not be used for labeling purposes and will be summarized with descriptive statistics.

For each subgroup, a logistic regression model will be fit that includes a fixed effect for subgroup membership. If the p-value for the subgroup term is less than 0.15, additional exploratory analysis may be performed to understand any variations in outcomes by subgroup. These analyses will be performed using the mITT Analysis Set as defined in Section 5.2, but will include available data only (with no imputation planned for missing outcome values).

Further, as a sensitivity analysis of the primary efficacy endpoint, subjects that start an OAB medication after sacral nerve stimulation and prior to the 6-month follow-up visit will be included in the analysis according to their actual outcomes, and the efficacy results will be summarized. Additional sensitivity analyses of the primary efficacy endpoint may be performed if deemed of interest. Such analyses will be considered exploratory.

5.6.3 Secondary Endpoints

The secondary endpoints completed at 6 and 12 months if not indicated differently are below:

s	tatistical Analysis Plan	Pa	ge 17 of 25
Sponsor	Study		Version
Neuspera	Neuspera Clinical Study of Neuspera's Implantable Sacral Nerve Stimulation (SNS) System in Patients with Symptoms of Urinary Urgency Incontinence (UUI)		17.0

- Change from baseline in quality of life as measured and assessed by the total ICIQ-OABqol score.
- Change from baseline in mean number of UUI episodes.
- The percentage of subjects who experience an improvement in UUI symptoms (therapy responders) of at least 50% or more at 12 months visit post implant.
- The percentage of subjects who experience an improvement in ICIQ-OABqol of at least 10 points.
- Change in urgent voids per day calculated across all diary episodes with at least mild urgency.
- Change in average number of daily voids from baseline in subjects with at least 8 voids at baseline.
- Change in quality of life measured from baseline as measured and assessed by the ICIQ-OABqol subscale scores.
- Comprehensive summary of all adverse events (AEs) for the duration of study participation.
- Device parameters including but not limited to voltage, pulse width, frequency, and stimulating electrode.
- Physician and subject satisfaction as assessed with the User Experience Questionnaire at 6month visit post implant.
- Change in Male/Female Lower Urinary Tract Symptoms questionnaire.
- The percentage of subjects with device-related serious adverse events reported through 12-month visit post-implant.
- Change in total urinary output as measured by 72-hour bladder diary.
- Change in fecal incontinence as measured by the Wexner Scale compared to baseline.
 Calculated in subjects with fecal incontinence.
- Patient Global Impression of Improvement (PGI-I) measured after implant during follow-up.

5.6.3.1 Analysis of Secondary Endpoints That May be Used for Labeling Claims

The primary analysis population for the secondary efficacy endpoints that may be used for labeling claims is the mITT analysis set as defined in Section 5.2. Section 5.6.4 describes missing data handling for these secondary efficacy endpoints in the mITT analysis set. These endpoints may also be assessed in other analysis sets without imputation for missing values.

S	tatistical Analysis Plan	Pa	ge 18 of 25
Sponsor	Study		Version
Neuspera	Clinical Study of Neuspera's Implantable Sacral Nerve Stimulation (SNS) System in Patients with Symptoms of Urinary Urgency Incontinence (UUI)		17.0

The type I error for the primary efficacy endpoint and for a subset of secondary endpoints will be controlled via hierarchical testing, in the order listed below.

The following secondary endpoints will be included in a hierarchical analysis of study endpoints and may be intended for labeling claims (all at 6-month visit post-implant follow-up):

- Change from baseline in mean number of UUI episodes
- Change from baseline in ICIQ-OABqol score
- The percentage of subjects who experience an improvement in ICIQ-OABqol of at least 10 points
- Change in urgent episodes per day from baseline. Calculated across all diary episodes with at least mild urgency
- Change in average number of daily voids from in subjects with at least 8 voids at baseline
- Change in fecal incontinence as measured by the Wexner Scale compared to baseline. Calculated in subjects with fecal incontinence.

For the ICIQ-OABqol, analysis will be conducted according to published scoring criteria (Coyne et al., 2002)^{iv}.

The statistical hypothesis tests for continuous endpoints will be based on comparing the mean change scores at 6 months or 12 months to 0. Mathematically, the null and alternative hypotheses are stated as:

Ho: $\mu \le 0$ Ha: $\mu > 0$

The statistical hypothesis test for the categorical endpoint based on UUI episodes will be based on comparing the percentage of subjects with a 50% improvement in UUI symptoms (therapy responders) at 12 months to a null value of 50%. Mathematically, the null and alternative hypothesis are stated as:

Ho: $p \le 0.50$ Ha: p > 0.50

The statistical hypothesis test for the categorical endpoint based on ICIQ-OABqol will be based on comparing the percentage of subjects with at 10 point improvement (the minimally clinically important

S	tatistical Analysis Plan	Pa	ge 19 of 25
Sponsor	Study		Version
Neuspera	Clinical Study of Neuspera's Implantable Sacral Nerve Stimulation (SNS) System in Patients with Symptoms of Urinary Urgency Incontinence (UUI)		17.0

difference, MCID; Coyne et al., 2006) at 6 or 12 months to a null value of 50%. Mathematically, the null and alternative hypothesis are stated as:

Ho: $p \le 0.50$ Ha: p > 0.50

The primary endpoint will be analyzed with a one-sided test at the α = 0.025 level. To maintain the overall type I error rate, testing of these secondary hypotheses will only proceed if the analysis for the primary efficacy endpoint is statistically significant (one-sided p < 0.025. If the primary efficacy analysis is not statistically significant (one-sided p ≥ 0.025), these secondary endpoints will not be formally tested, and analysis of these endpoints will be considered exploratory.

Provided that the primary endpoint analysis is statistically significant, testing will proceed to the secondary endpoints included in the hierarchical analysis. Testing will proceed in the order specified above with each endpoint tested sequentially. If the analysis of the secondary endpoint under consideration is statistically significant (one-sided p < 0.025, the result for that endpoint is declared statistically significant, and testing proceeds to the secondary endpoint next in the order. As soon as an analysis is not statistically significant (one-sided $p \ge 0.025$), that endpoint is declared statistically non-significant, further testing of these secondary endpoints is terminated, and no formal statistical conclusion is reached on the remaining endpoints, irrespective of their observed p-values. Subgroup analysis of the secondary endpoints will be performed for the following subgroups: sex, age (Age<65, Age≥65), race (white vs. non-white), baseline UUI episodes, site, and region (US vs. OUS). The subgroup analyses of the secondary efficacy endpoints are regarded as exploratory and will not be used for labeling purposes and will be summarized with descriptive statistics.

The sponsor intends to file a PMA submission at the end of the six-months of follow-up if the null hypothesis associated with the primary efficacy endpoint is rejected. This will include analysis of the primary endpoint and the first secondary endpoint in the hierarchical sequence. If the analysis of the first secondary endpoint is statistically significant, the remaining secondary endpoints in the sequence will be analysed in order when the data are available.

5.6.3.2 Secondary Endpoints not Intended for Labeling Claims

Analysis of secondary endpoints not intended for labeling claims, (i.e., those secondary endpoints not included in the hierarchical testing in Section 5.6.3.1) will be considered exploratory in nature. Each of these endpoints will be tested at the α = 0.05 level using a two-sided test with no adjustment for multiplicity. Any p-values from these analyses will not be reported in the labeling.

S	tatistical Analysis Plan	Pa	ge 20 of 25
Sponsor	Study		Version
Neuspera	Neuspera Clinical Study of Neuspera's Implantable Sacral Nerve Stimulation (SNS) System in Patients with Symptoms of Urinary Urgency Incontinence (UUI)		17.0

5.6.4 Handling of Missing Data

All attempts will be made to limit the amount of missing data. No attempt will be made to impute missing data for any analyses except for the primary and secondary efficacy endpoints as specified below in the mITT analysis set. If a data point is missing, that data point will not contribute to that portion of the analysis. The number of evaluable observations will be reported in the analysis so that extent of missing data can be assessed.

For the following efficacy endpoints, subjects withdrawing for reasons related to a lack of efficacy or due to an adverse event (including death) will be counted as failures if they do not have evaluable data for the endpoint:

- The percentage of all implanted subjects who experience an improvement in UUI symptoms of 50% or more at 6-month post-implant (primary efficacy endpoint)
- The percentage of all implanted subjects who experience an improvement in UUI symptoms of 50% or more at 12-month post-implant (secondary efficacy endpoint)

For the continuous efficacy endpoints that may be used for labeling claims, no change from baseline values will be assumed for subjects withdrawing for reasons related to a lack of efficacy or due to an adverse event (including death) if they do not have evaluable data for the endpoint.

If data on these endpoints are missing for other reasons (missing diary or ICIQ-OAB questionnaire, subject loss-to-follow-up, etc.), multiple imputation will be used to impute the outcome. Results from the imputed data sets will be combined appropriately to preserve valid inference. A tipping point analysis will also be performed, examining outcomes for the primary efficacy endpoint for all possible permutations of imputed values for missing subjects.

Multiple imputation will be based on the following variables and will use full conditional specification and 100 imputed data sets. Variables to be included in the imputation model include:

- baseline age, investigational site, baseline UUI episodes, and all available follow-up visit UUI
 episodes through 6 months or 12 months (for the primary and secondary efficacy endpoints of
 improvement in UUI)
- baseline age, investigational site, baseline score, and all available follow-up visit scores through 6 months or 12 months (for the remaining secondary efficacy endpoints that may be used for labeling claims)

S	tatistical Analysis Plan	Pa	ge 21 of 25
Sponsor	Study		Version
Neuspera	a Clinical Study of Neuspera's Implantable Sacral Nerve Stimulation (SNS) System in Patients with Symptoms of Urinary Urgency Incontinence (UUI)		17.0

If there are fitting issues due to the separation or quasi-separation of data points, an augmented likelihood approach will be used.

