Of the 34 subjects implanted with the neurostimulator, only one subject was a non-responder after 2-hours of daily stimulation. This subject was a responder after an additional 14-days at 4 hours of daily stimulation and continued into the post-trial follow-up phase. There have been twelve device explants in the trial and two subjects exited the trial without device explant (one due to lost-to-follow-up, one due to an adverse event of dementia). Eleven subjects requested explant due to therapy not producing desired effect or unsatisfied with therapy or device performance, and one subject was explanted due to non-compliance.

Phase I responders will continue to be followed until US PMA approval. European approval, CE Mark, may be achieved earlier or later than PMA approval is achieved which may be 36 months or longer post trialing period for some subjects; however, all subjects will be followed until US PMA approval. If Neuspera determines that regulatory approval will not be achieved, the trial will be closed. If regulatory approval is achieved, the subjects may be approached to continue participation in a post market clinical study and will be provided a separate informed consent at that time.

Phase I Sub-Study: There is a sub-study to investigate the effectiveness and subject acceptance of half-hour daily stimulation to treat UUI. The details are provided in Appendix A: Phase I Sub-Study.

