#### 7.5.8.11 Post-Explant 30-Day Follow-up

A 30-day follow-up visit is required for all subjects where the implant procedure was attempted but the device was not implanted or where the device was explanted. The following measures are required:

- Vitals signs
- Changes to medication (including OAB medications) and OAB therapies
- Adverse event assessment
- Wound check

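### PGI-I and subject satisfaction are summarised on observed cases and are not collected at explant, so the reported percentages are likely to be biased upward by an unknown amount

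*SAP*

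**What the plan says.** SAP 5.6.3 lists both measures as secondary endpoints: "Physician and subject satisfaction as assessed with the User Experience Questionnaire at 6month visit post implant" and "Patient Global Impression of Improvement (PGI-I) measured after implant during follow-up". Neither is in the hierarchy of SAP 5.6.3.1. SAP 5.6.3.2 therefore treats both as exploratory and keeps their p-values out of the labeling; it names no analysis population for them.

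On missing data, SAP 5.6.4 states: "No attempt will be made to impute missing data for any analyses except for the primary and secondary efficacy endpoints as specified below". The endpoints then specified are the 6- and 12-month UUI responder rates and the endpoints that may be used for labeling claims. For the rest, "If a data point is missing, that data point will not contribute to that portion of the analysis", with this safeguard: "The number of evaluable observations will be reported in the analysis so that extent of missing data can be assessed".

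On collection in Phase II, the subject questionnaire is taken at Day 28 or Day 42 and at Month 6 (Protocol 7.5.9.15). PGI-I is taken at Months 3, 6, 12, 24 and 36 (Table 9). Under Protocol 7.4.4, an implanted subject who leaves is explanted, has a 30-day follow-up and exits. Protocol 7.5.8.11 says "A 30-day follow-up visit is required for all subjects where the implant procedure was attempted but the device was not implanted" and extends the same visit to explanted subjects. Its required measures are vital signs, medication changes, adverse events and a wound check. The explant data list in Protocol 7.5.8.10 contains neither form.

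**The concern.** Someone who has the device removed because it does not help, or because they are unhappy with it, is the person most likely to answer not improved or not satisfied. As scheduled, that person has no form to complete at explant or exit and is not counted at later visits. The missingness then depends on the outcome being measured, and the observed percentage tends to describe those who chose to keep the device.

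Phase I shows that this route out is real: "Eleven subjects requested explant due to therapy not producing desired effect or unsatisfied with therapy or device performance", out of twelve explants in all. The plan guards other endpoints against the same loss. SAP 5.7 makes any permanent explant before the primary assessment a failure. SAP 5.6.4 assumes no change on the continuous labeling endpoints after withdrawal for lack of efficacy or an adverse event. PGI-I and satisfaction have no counterpart to these rules.

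What is at stake is how patient acceptance is reported for a device worn for hours each day. SAP 5.6.3.2 keeps p-values out of the labeling but does not restrict the percentages.

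**Working it through.** The documents give no satisfaction or PGI-I rate and no cut-off for a favourable answer, so there is no stated figure to reproduce. The check has two parts.

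**1. Is the loss likely to depend on the outcome?**

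- Phase I: 34 implanted and 12 explants, of which 11 were for lack of effect or dissatisfaction and 1 for non-compliance (Protocol Synopsis, Phase I; 3.1.2.2.1). 11/34 = 32.4% of those implanted.
- Phase II: 12 explants, reported alongside 130 implant attempts (Protocol 3.1.2.2.2). 12/130 = 9.2%. Reasons and timing are not given.

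Phase I supports the direction of the bias. It says little about size at Month 6, because its explants accrued over a long follow-up: the Appendix A sub-study (section 2.3) places all Phase I subjects beyond Month 48.

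**2. How large could the gap be?**

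Let N be all subjects, k those without data who would have answered unfavourably, and S the favourable proportion among those who answer. Assume everyone else answers.

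- Observed-case rate = S
- All-subject rate = S × (N − k) / N
- Gap = S × k / N

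S and k are assumptions; N = 130 attempts. Entries are the all-subject rate, with the gap in points in brackets.

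| k missing | S = 60% | S = 70% | S = 80% | S = 90% |
|---|---|---|---|---|
| 3 | 58.6% (1.4) | 68.4% (1.6) | 78.2% (1.8) | 87.9% (2.1) |
| 6 | 57.2% (2.8) | 66.8% (3.2) | 76.3% (3.7) | 85.8% (4.2) |
| 12 | 54.5% (5.5) | 63.5% (6.5) | 72.6% (7.4) | 81.7% (8.3) |

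Example: S = 80%, k = 6 gives 0.80 × 124/130 = 76.3%, and 0.80 × 6/130 = 3.7 points.

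With implanted subjects as the base, the 95% planning success rate gives 0.95 × 130 = 123.5, about 124 (also an assumption). With k = 12 the gap is then 0.60 × 12/124 = 5.8 points to 0.90 × 12/124 = 8.7 points, so the choice of base matters little.

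The k = 12 row is an upper case for the reported explants. It requires all twelve to have occurred before the visit analysed, to have left no data, and to have been unfavourable.

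**The case against.** The case against has real weight.

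- **Withdrawal data are promised.** Protocol 7.4.4 undertakes to make all attempts to collect primary and secondary endpoint data from subjects who withdraw early. A reader might infer that only subjects still attending can be counted; the documents do not say that. Nor does SAP 5.1.3 exclude a form obtained at withdrawal: it assigns data to the nominal visit entered in the CRF. This stands, and it softens the point. But no scheduled visit or form carries out the undertaking for these two instruments, and the SAP does not say how such a form would be used.
- **No rate exists to be wrong.** PGI-I is a single 7-point item (Protocol 7.5.9.3.4), and no threshold for improved or satisfied is defined. A reader might conclude that the rates are too high as a matter of fact. The documents support only a likely direction.
- **Timing may limit the effect.** A subject explanted after Month 6 can already have answered at Month 6. The one Phase I explant whose course is described (Protocol 3.1.2.1) followed six months of follow-up. This stands for Month 6 but helps less for PGI-I at Month 12 and later.
- **The shortfall is visible.** Evaluable numbers are reported, and SAP 5.3 summarises early exits by reason. That shows how many are missing and why they left, but it does not adjust the percentage.
- **Other acceptance data exist.** There is a questionnaire at Day 28 or Day 42, and the stimulation diary records how difficult consistent stimulation was to achieve (Protocol 7.5.9.5). So these two endpoints are not the only evidence on acceptance. The early questionnaire, however, precedes any later loss of effect.
- **The endpoints are exploratory.** This is correct, and it is why this is only a minor improvement.

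**Conclusion.** The point holds as a likely upward bias of unknown size in two exploratory summaries. It rests on three documented facts: an observed-case rule, no scheduled collection at explant or exit, and a Phase I record in which 11 of 12 explants were for lack of effect or dissatisfaction.

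The size depends on assumptions the documents cannot settle: the favourable rate among those who answer, how many Phase II explants fall before the visit analysed, their reasons, and how many withdrawal forms are in fact obtained. Over the range shown, the gap is about 1 to 4 points for 3 to 6 missing of 130, and up to about 8 points if all 12 are missing and unfavourable.

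Two stronger readings should be avoided. The Phase I proportion of 32.4% should not be carried over to Phase II at Month 6, and not every explant should be taken as a dissatisfied subject, since one in Phase I was for non-compliance. Study success, the primary test and the hierarchy are not affected.

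**What to change.** In SAP 5.6.3 and 5.6.4, keep the observed-case distribution and add beside it a summary of PGI-I (improved or not) and subject satisfaction (satisfied or not):

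- State both cut-offs before the data are analysed.
- Use all implanted subjects as the denominator.
- Count a subject with no data at the visit as not improved and not satisfied if withdrawn or explanted for lack of efficacy, dissatisfaction or an adverse event.
- Show explants for other reasons separately.
- State how a form obtained at withdrawal under Protocol 7.4.4 is assigned to a visit.

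This needs no new data: exit reasons (Protocol 7.4.4) and explant reasons (Protocol 7.5.8.10) are already recorded. The cost is a few sentences in the SAP and one extra table. The downside is a slightly lower reported percentage.

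Optionally, add the two existing forms to the explant visit in Table 9. With 130 attempts already reported against a planned 120, this can help only with explants still to come.

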5.7 Analysis of Replacements, Explants

During the course of the study, it may be necessary for the investigational device to be replaced or permanently explanted from the subject. Revision rates in the literature range from 4% in the InSite studyⁱⁱ to 33% in the Herbison^{vi} study. Depending on the timing of replacements, it may be necessary for the subject's response rate to be reassessed in the first 28 to 42-days post-implant.

During Phase I of the study, if a subject receives a neurostimulator replacement prior to Month 3 clinic visit, the subject will restart their follow-up schedule, and repeat the trialing period and any of the follow-up visits completed prior to replacement. If a subject receives a device replacement prior to the assessment of the primary efficacy endpoint in Phase II (Month 6 clinic visit), the subject will restart their entire follow-up schedule post-implant, including the responder rate assessments at Day 28 and Day 42, if not a responder at Day 28. The date of replacement will be considered the new Device Implant date for analysis and follow-up purposes. If a device replacement is required after the follow-up periods indicated above, subjects will continue on their original follow-up schedule and do not repeat any of the assessments or follow-up visits already completed.

If assessment of the response rate is repeated in the first 28 to 42-days post-implant, data collected after the most recent implant will be used in the analysis. Similarly, if the subject is required to repeat any portion of the post-implant follow-up visits after a replacement (replacement occurred before Month 6 clinic visit), the data from the replacement visit(s) will be used in analysis. The date of replacement will be considered the Device Implant date for analysis and follow-up purposes. A subject is only allowed to repeat any portion of the post-implant period once.

If the device is permanently explanted prior to the assessment of the primary efficacy endpoint for any reason, the subject will be considered a failure for the primary efficacy analysis.

